1.0 Project Summary/Abstract

Due to the age associated sarcopenia and reduced cardiovascular fitness, frail older adults experience significant decrease in physical function which comprises of mobility, endurance, muscle strength and balance control [1,2,3]. The impaired physical function results in poor quality of life and reduced community participation, leading to increased frailty and long-term disability [8]. Further, compared to cognitively intact frail older adults, cognitively impaired frail older adults experience greater deterioration of such physical function, specifically during dual-task performances (i.e., simultaneous performance of cognitive and motor task). This deterioration occurs due to increased cognitive-motor interference as a result of dual-tasking and is known to increase exhaustion among frail older adults [7]. Previous studies have used multicomponent training and have shown to improve physical function and maintain cardiovascular functioning [4,5,6]. However, the capacity of such interventions to improve cognitive function along with physical function is not known or unclear. Further, the concurrent comorbidities that occur along with psychosocial issues such as depression present as barriers and lead to reduced compliance to therapy leaving only a few of them to benefit from it [40,41]. Alternate forms of therapy such as exergaming with explicit cognitive training has shown promising effects in improving motor and motor function in disabled populations [38,39]. These studies use a cost-effective, off the shelf device such as Nintendo Wii or Microsoft Kinect to deliver the training which is easily available and Further, such training has demonstrated increase in brain clinically translatable. connectivity enhancing cognitive functions associated with balance control [10]. However, there is limited literature examining the effect of exergaming in older frail population and the efficacy of such training is unknown. Therefore, this study proposes a randomized controlled trial to examine the feasibility of CogXergaming program with an aim to improve locomotor-balance control, cognition, muscular system and cardiovascular fitness.

2.0 Background/Scientific Rationale

The population of adults aged 60 years and older has been growing with around half of the people older than 85 years estimated to be frail [14,15]. Age-related changes in multiple systems affecting balance, mobility, muscle strength, motor processing, cognition, nutrition, endurance and physical activity (PA) results in frailty [3]. Studies on frail older adults have reported improvement in mobility and functional level following exercise interventions [16]. Regular physical activity in this population has helped improve cardiovascular conditioning and quality of life, thus allowing these frail older adults a chance at independent living in the community [17,18,19,20,21]. In addition to physical comorbidities, the presence of psychosocial issues such as depression may act as a barrier to community participation. Several PA interventions have demonstrated limited long-term effect and sustainable behavioral change in this population [22,23]. An evidence-based fall prevention program called Matter of Balance (MOB) was developed to reduce fall risk and improve physical function and maximize activity participation in older adults [11,12,13]. Meanwhile, Exergaming, a task-specific interactive gaming, has been gaining attention as a novel therapeutic alternative that promotes motor recovery in healthy and disabled populations [24,25,26]. Exergaming involves repetitive-task specific exercises with movement execution feedback and motivation provided in real time [22,24,25,26]. Studies have shown Exergaming improved symmetrical weight shifting, multi-directional stepping, single-stance, rapid movement training and selfinitiated postural weight shifts in the participants [27,28]. This anticipatory postural significantly improve control training helps balance control mobility [8.24,26,27,28,29,30]. In addition to the physical function domains that underlie physical frailty, executive cognitive domain functions also predict late-life physiological impairments [31]. Thus, we postulate that PA facilitated through Exergaming and accompanied by simultaneous cognitive training is a novel approach to counter and inhibit frailty associated with physical function and cognitive decline.

3.0 Objectives/Aims

Aim 1: To test the feasibility (compliance and effectiveness) of cognitive-motor exergaming (CogXergaming) in the frail older adults and to compare the improvements in behavioral biomarkers in this group across balance, muscle fitness, cardiovascular fitness and global cognition to the group receiving the Matter of Balance training.

Hypothesis: Participants will respond well to CogXergaming training paradigm and demonstrate significant improvements in balance, muscular fitness, cardiovascular fitness and global cognition as compared to the Matter of Balance training group.

Aim 2: To examine the effect of CogXergaming on physical activity levels and quality of life measures post-intervention.

Hypothesis: The participants who received CogXergaming will demonstrate significant improvement in physical activity and quality of life post-training as compared to their own pre-training scores.

Aim 3: To examine the effect of CogXergaming structural and functional connectivity within the cognitive-motor areas pre and post training to establish effect size.

Hypothesis: Post-training, participants will demonstrate improved memory consolidation, attention, motor planning and execution compared to pre-training indicating improved functional connectivity within the cognitive-motor areas.

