6.0 Study Design and Procedures

- This study will be a randomized controlled design.
- During the telephone screening, all the participants will be asked to choose a group that
 they prefer to participate which includes 3 options: Group 1: In-person assessments
 and in-person training; Group 2-In-person assessments and online training and Group
 3- Online assessments and online training.

[figure not shown]

- Figure 1 above shows recruitment and distribution of participants into differenct groups based on the options given for assessment and training to the participants during telephone screening.
- After the participants are allocated to groups 1,2 and 3 depending on their choice, each
 participant from every group will be randomly assigned either Group A (CogXergaming)
 or Group B (Matter of balance) for training by flipping a coin.
- Al the participants will be undergo 1-on-1 testing and training.
- Study protocol will vary according to the groups that the participants choose to be in (Groups 1,2 or 3).
- For Group 1 (In-person assessments and in-person training): Group A (CoXergaming) will undergo a total of 8 weeks session with first week and last week comprising of assessment. 6-week training will be delivered using the Nintendo Wii-Fit gaming system and a pointer mouse. Participants will visit the laboratory 3 times a week for 6 weeks with each session lasting for 60 minutes (18 training sessions). During training session, participants will wear a gait belt and will be guarded by a research assistant for safety. On the other hand, if the Group 1 participant gets assigned to Group B (Matter of balance) then participants from Group B will undergo a total of 10 weeks session with first week and last week comprising of assessment. The participants will undergo an 8-week (one session a week for 2 hours/day, 8 sessions in total) structured intervention specifically designed to reduce the fear of falling and to increase the engagement in PA.

| Test | Pre- test | CogXergaming/TeleXercise Intervention (6 weeks) | | | | | | | | | | | Post-test | | | | | | | |
|---------|--------------|---|---|---|---|---|---|---|---|---|----|----|-----------|----|----|----|----|----|----|-----|
| Session | 1-4 | 1 | 2 | 3 | 4 | 5 | 6 | 7 | 8 | 9 | 10 | 11 | 12 | 13 | 14 | 15 | 16 | 17 | 18 | 1-3 |
| Week | 1 | 2 | | 3 | | 4 | | 5 | | 6 | | | 7 | | | 8 | | | | |

| Test | Pre-test | M | latte | Post-test | | | | | | |

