6.4 Outcomes

Assessment: The following tests will be administered as baseline and post-intervention. Table 1: Assessment variables for Groups 1 and 2 (In-person assessment) and Group 3 (Online-assessment)

| Group 1 and 2 Assessments (In-person assessment) | Group 3 Assessments (Online Assessment) | | | | | | |
|--|---|--|--|--|--|--|--|
| Balance Intentional balance control (Limits of stability test) (single and Dual task conditions) Postural control (sensory organization test) (single and Dual task conditions) Reactive balance control (Stance perturbation test) (single and Dual task conditions) NIH balance Toolbox (Standing balance test) Gait GaitRite mat (single and Dual task conditions) NIH Balance toolbox (4m walk Gait speed test) | Balance - 30-second chair stand test - Four-step square test - Sharpened Romberg's - One leg stance test Gait - Tinetti Performance Oriented Mobility Assessment | | | | | | |
| Muscular fitness - Isokinetic Dynamometer - B-mode Ultrasonography Cardiovascular fitness - Heart rate variability - YMCA submaximal cycle Ergometer test - NIH Balance toolbox (2-minute walk endurance test) | Cardiovascular fitness - 2-minute step in place test | | | | | | |
| Cognitive performance - Neuropsychological battery tests - NIH cognitive toolbox - Auditory clock test and letter number sequencing (single and Dual task conditions) Physical activity and motivation - Smartphone (Android/iphone) | Cognitive performance - Neuropsychological battery tests - NIH cognitive toolbox - Auditory clock test and letter number sequencing (single and Dual task conditions) Physical activity and motivation - Smartphone (Android/iphone) | | | | | | |

| fMRI scanning | - |
|---|---|
| - Intrinsic motivational index | - Intrinsic motivational index |
| - Physical activity scale for the elderly | - Physical activity scale for the elderly |
| - Quality of life (SF-36) | - Quality of life (SF-36) |
| - Wearable sensor | - Wearable sensor |
| | |

Aim 1: Balance and Gait tests:

Balance:

For In-Person Assessment (Group 1 and 2)

Intentional balance control

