Visual Stroop test is a demonstration of interference in the reaction time of a task. In this test, the participant will be asked to read the ink color in which the word is printed and not read the word. Auditory Stroop- The participant will hear words "High" and "Low" at high or low pitches. His/her task is to respond to the pitch of the word and not repeat the word. The responses will be audio recorded. Flanker inhibitory control and attention test- In this test, the participant is instructed to verbally respond right or left that matches the direction of the middle arrow in the stimulus given on the screen. Accuracy of the responses are recorded. List Sorting Memory test- The test is divided into two subsets to evaluate working memory. The participant will be shown a picture of animals. For the first subset, the task for the participant is to name the animals from smallest size to the largest size. The second subset involves a category of food along with pictures of animals. The task of the participant is to say the food first and then name the animals from smallest size to the largest size. The accuracy of the participant's response will be audio recorded. **Dimensional Change card sort**- This test involves three subsets assessing executive functioning. For the first subset, the participant is expected to say the same shape of the stimulus provided, for example, if the stimulus given is a boat, and for the answers from which the participant is supposed to choose is given as rabbit and boat, he is expected to say "boat". In the second subset, the participant is expected to say the object that matches the color of the stimulus and avoid naming the shape. The last subset involves playing the first and the second subset together. Pattern comparison Processing speed test- This test involves the participant to say the yes or no depending on the pictures provided look the same or not. The similarity of shapes of objects, colors are provided as stimulus. This test evaluates the processing speed of cognitive functioning.

Aim 2: Physical Activity (PA) Level

For In-Person Assessment (Group 1, 2 & 3)

Physical activity will be monitored using a wearable device or a smartphone to track the number of steps performed weekly pre and post the intervention. Participants will also be asked to visit the lab bi-weekly to upload their data upload.

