12.0 Statistical Considerations

Counting for the attrition rate of 20% of most of the interventions with frail older adults, we expect to use data of 96 participants with 16 participants in each subgroup (Group 1A and B; Group 2A and B; Group 3A and B) for data analysis. To determine the effect of training using Exergaming, pre-post changes of balance, cognitive, gait and cardiovascular measures will be examined by ANCOVA. Results of the study from a sample size of 96 will enable us to conduct power analysis to plan for a larger scale RCT.

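### Aim 2 is framed as the effect of CogXergaming on physical activity and quality of life, but its hypothesis tests only arm A's own pre-post change, and no A-versus-B analysis of these outcomes is given

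*Combined protocol and SAP*

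**What the plan says.** In Section 3.0, Aim 2 concerns the effect of CogXergaming on physical activity levels and quality of life. Its hypothesis is that those who received CogXergaming "will demonstrate significant improvement in physical activity and quality of life post-training as compared to their own pre-training scores". The Aim 1 hypothesis in the same section is stated between arms: participants will "demonstrate significant improvements in balance, muscular fitness, cardiovascular fitness and global cognition as compared to the Matter of Balance training group".

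Section 6.0 calls the design randomized and controlled. Within each delivery preference (Groups 1, 2 and 3), participants go to Group A (CogXergaming) "or Group B (Matter of balance) for training by flipping a coin". Matter of Balance is described there as a "structured intervention specifically designed to reduce the fear of falling and to increase the engagement in PA".

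Section 6.4 introduces its assessments with "The following tests will be administered as baseline and post-intervention". Table 1 lists smartphone and wearable step recording, PASE and SF-36 for all three delivery groups and does not divide them by arm. The Aim 2 text adds that devices will "track the number of steps performed weekly pre and post the intervention".

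The only analysis sentence is in Section 12.0: "pre-post changes of balance, cognitive, gait and cardiovascular measures will be examined by ANCOVA". Section 9.0 simply refers the reader there.

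**The concern.** Aim 2 asks a causal question and its hypothesis answers a different one. If the hypothesis is followed, a significant rise in steps, PASE or SF-36 within arm A would be read as the effect of CogXergaming. At least five other explanations are open:

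- the passage of time;
- repeat measurement;
- wearing and reading an activity monitor;
- regression to the mean, because Section 6.1 admits only people reporting under 3 hours of activity a week;
- a benefit shared with Matter of Balance, which is itself meant to raise activity.

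Randomization is there to remove what the arms share, and the stated contrast does not use it. The consequence reaches past this study, because Section 12.0 intends the results to feed the power analysis of a larger randomized trial, which would need a between-arm difference.

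**Working it through.** **The plan's own figure.** 120 enrolled with 20% attrition gives 120 × 0.80 = 96 analysed. 96 / 6 subgroups = 16, so 3 × 16 = 48 per arm. This reproduces Section 12.0. The 48 is nominal, because allocation is by coin flip. Binomial(96, 0.5) has 2.5th and 97.5th percentiles of 38 and 58, assuming equal attrition by arm.

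**Where a comparison could be stated.** Section 3.0 gives arm A against itself. The Aim 2 part of Section 6.4 describes measurement only. Section 9.0 gives a cross-reference. Section 12.0 gives an ANCOVA whose list contains neither physical activity nor quality of life. No A-versus-B analysis of these outcomes appears.

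**Illustration of the mechanism.** The documents give no test, significance level, correlation or expected drift for Aim 2. I assume two-sided 0.05, outcomes in units of their SD, pre-post correlation r, and a drift D over arm A's interval that owes nothing to treatment.

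*Pre-post test in arm A.* Paired t-test, n = 48, 47 df. SE = sqrt(2(1 − r)) / sqrt(48), which is 0.144, 0.112 and 0.065 at r = 0.5, 0.7 and 0.9. The noncentrality is D / SE, for example 0.2 / 0.144 = 1.39.

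*A versus B.* ANCOVA of the post score on baseline, arm and Group 1/2/3, with 96 − 5 = 91 df. SE = sqrt(1 − r²) × sqrt(1/48 + 1/48), which is 0.177, 0.146 and 0.089. If drift is equal in both arms it cancels and the error rate is 5%.

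*Unequal timing.* For Group 1, Section 6.0 puts the arm A post-test in week 8, while "participants from Group B will undergo a total of 10 weeks session with first week and last week comprising of assessment". The 6-week and 8-week training periods imply the same gap in Groups 2 and 3. From week 1 the intervals are 7 and 9 weeks. Linear drift then leaves D × (9 − 7)/7 = 0.03, 0.06 or 0.09 SD between arms.

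Chance of a significant result when there is no treatment effect, for D = 0.1 / 0.2 / 0.3 SD:

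| r | Pre-post in arm A | A versus B, equal drift | A versus B, linear drift, weeks 8 and 10 |
|---|---|---|---|
| 0.5 | 10 / 27 / 53% | 5% | 5 / 6 / 8% |
| 0.7 | 14 / 42 / 75% | 5% | 5 / 7 / 9% |
| 0.9 | 33 / 86 / 99.5% | 5% | 6 / 10 / 16% |

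At r = 0.5, the pre-post rates are 9 / 22 / 44% with 38 in arm A and 12 / 32 / 61% with 58.

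**Cost in precision.** The 95% CI half-width is the t quantile times SE (1.986 on 91 df, 2.012 on 47 df). At r = 0.5, 0.7 and 0.9 it is 0.351, 0.290 and 0.177 SD between arms, against 0.290, 0.225 and 0.130 SD pre-post. The ratios are 1.21, 1.29 and 1.36.

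**The case against.** The best defence is that this is a declared choice in a pilot. Aim 1 carries the between-arm contrast, Aim 2 openly says it looks at change from participants' own baseline, and no confirmatory claim is attached. A within-arm description is a legitimate pilot output. This stands to the extent that rewording Aim 2 as descriptive is an acceptable remedy. It does not rescue the present text, which speaks of the effect of CogXergaming and predicts a significant improvement.

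A second objection is that A minus B answers another question: benefit relative to an active programme that also targets physical activity. That is correct. The contrast removes shared true benefit along with drift, so a null difference would not show that CogXergaming does nothing. This limit should be stated, but it does not make the pre-post contrast causal.

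Third, the between-arm comparison is not clean. Post-test timing differs, and at high correlation the error rate under linear drift reaches 16%. It remains far below the pre-post rate in the same setting.

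A reader might go further and infer that activity monitoring acts on arm A alone, so that its influence could not cancel. The documents do not support that. Sections 6.3, 6.4 and 8.0 provide monitors and step read-outs without restricting them to arm A. Only the coach's feedback after each session, described in Section 6.2 for online CogXergaming and not for Matter of Balance, differs as documented.

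**Conclusion.** The point holds as a mismatch between aim, hypothesis and analysis, and should be corrected before analysis. It rests on the Aim 2 hypothesis sentence and on the absence of any A-versus-B analysis of these outcomes, and does not depend on the illustrative figures. Those depend on an assumed paired t-test, two-sided 0.05, 48 completers per arm, and chosen drifts and correlations. They show how the error arises and do not forecast this trial's error rate.

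Two stronger readings are not supported. A reader might take the omission from the Section 12.0 list as proof that physical activity and quality of life were deliberately left out of the between-arm analysis. That list also omits muscular fitness, which Aim 1 does compare between arms, so the omission is weak evidence. A reader might also infer a design fault, with no control data for Aim 2. Table 1 schedules steps, PASE and SF-36 in both arms, so the fault lies in the stated contrast and not in the design.

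**What to change.** State the Aim 2 hypothesis in Section 3.0 as CogXergaming versus Matter of Balance. In Section 12.0, extend the ANCOVA (post score on baseline, arm and Group 1/2/3) to weekly pre and post steps, PASE and SF-36, and report the adjusted difference with its 95% CI. Specify the weekly counts, because Section 6.4 also describes steps per training session. Include the Community Integration questionnaire and the Geriatric Depression Scale once a baseline is confirmed; Section 6.4 names both under quality of life, but Table 1 lists neither. Keep within-arm change as descriptive.

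If the sponsor prefers to keep only the within-arm comparison, reword Aim 2 as descriptive change and make no claim of a CogXergaming effect.

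State these limits with the between-arm result:

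- It is relative to an active programme, so a null result does not show that CogXergaming has no effect.
- Post-test timing differs by arm, so record the actual interval.
- The extra coach feedback in online arm A may not cancel.

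The cost is wording in Sections 3.0 and 12.0 and one added analysis. No new data are needed for the outcomes in Table 1. At a nominal 48 per arm the between-arm interval is about 21-36% wider than the pre-post one.

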4.0 Eligibility

- Community dwelling frail older adults aged 60 years or above
- Can understand & communicate in English
- Ability to walk more than 30 feet with or without an assistive device
- Ability to stand 5 minutes without an assistive device (length of a Wii Fit game)

5.0 Subject Enrollment

A total of 120 participants will be enrolled in the pilot study (see Research Design and Procedures for details).

We will initially recruit the participants by posting flyers (approved by the Institutional Review Board) at Geriatric and internal medicine by contacting [name], giving presentations to potential participants at various exercise centers and senior homes. We will also use social media, such as Facebook, Twitter, etc. to post flyer for recruitment. As a part of recruitment procedure, we will not be accessing the EMRs, and will get referrals from different physicians for those who are potentially eligible to participate in our study. Our research staff team will travel to various locations to provide the background education about our study and explain the procedures through the study involved and will show them the consent form. The consent form will provide enough information about the study and the interested people will be asked to provide their contact information, which will be noted down on a sheet. Later, one of the researchers mentioned on the Appendix P will contact them for a telephone screening. Individuals making the initial contact looking at flyers will also undergo the same telephone screening question and will be asked where they heard/read about the study. The initial telephone screening would determine their general health condition, preliminary eligibility. They will be asked to choose a group that they prefer to participate which includes 3 options- 1) Group 1: In-person assessments and inperson training (where all the tests and training sessions will be conducted in the laboratory); 2) Group 2: In-person assessments and online training (where only the tests before and after training will be conducted in the laboratory and they

[figure not shown]
can do the 1-on-1 training online at home via zoom application); Group 3: Online assessments and online training (where all the tests and training will be conducted online via zoom application). Those who choose to be in Group 1 or Group 2, they will be screened for claustrophobia using the claustrophobia questionnaire (Napp, A. E. et al 2016) and individuals who score an average of 1.2 or less will be given the option of being included for fMRI study participation. Once he/she meets the inclusion criteria, they would be scheduled for an in-person laboratory screening at Room 415, B56 or 725 of the College of Applied Health Sciences building. The laboratory screening involves evaluating the individual's performance on various clinical measures balance, muscle strength, endurance and cognition. The participants will also undergo osteoporosis screening using an ultrasound device to measure their heel bone density. During the bone density testing, their heel will be squeezed by the rubber membranes of the testing apparatus. As a result, they will experience some pressure, and/or mild tingling, cold or warm sensation on the heel from the membranes or the gel used during the testing. While Group 3 will continue with online test measures followed by training sessions.

All participants' information will be recorded in a database in the form of an excel sheet that will include the information of the participants eligible and those not eligible for study. For participants not eligible for the study, the reason for withdrawal or exclusion from the study participation as per the telephonic interview will be recorded. An excel file would be maintained to document the results of participants' initial telephone screening, osteoporosis screening, clinical assessment and laboratory dynamic stability test.

To minimize coercion and undue influence on the participants, the potential participants will directly call research coordinators in response to a flyer and/or other recruiting materials or by word of mouth. In case of interested participants referred by the physician or met at recruitment meetings, the researcher will collect the contact information and will initiate contact to perform a telephonic screening. Participation is voluntary and individuals' decisions will not be influenced by research personnel who conduct pre- or post-training assessments.

